8.3 Subject Confidentiality

To protect subjects' confidentiality, all subjects and their associated samples will be assigned numerical study identifiers or "codes." No identifiable information will be provided to AbbVie.

9 SOURCE DOCUMENTS AND CASE REPORT FORM COMPLETION

The investigator is responsible for ensuring the accuracy, completeness, legibility, and timeliness of the data reported. All source documents should be attributable, legible, contemporaneous, original, accurate, and complete to ensure accurate interpretation of data. Clinical site monitoring is conducted to ensure that the rights and well-being of human subjects are protected, that the reported trial data are accurate, complete, and verifiable, and that the conduct of the trial is in compliance with the currently approved protocol, ICH Good Clinical Practice (GCP), and applicable local regulatory requirement(s). During the COVID-19 pandemic, remote monitoring of data may be employed if allowed by the local regulatory authority, IRB/IEC, and the study site.

10 DATA QUALITY ASSURANCE

AbbVie will ensure that the clinical trial is conducted with a quality management system that will define quality tolerance limits to ensure human subject protection and reliability of study results. Data will be generated, documented, and reported in compliance with the protocol, ICH GCP, and applicable regulatory requirements.

11 COMPLETION OF THE STUDY

The end-of-study is defined as the date of the last subject's last visit or date of the last follow-up contact, whichever is later.

APPENDIX A. STUDY SPECIFIC ABBREVIATIONS AND TERMS

Abbreviation	Definition
AE	adverse event
ALC	absolute lymphocyte count
ALT	alanine aminotransferase
AML	acute myeloid leukemia
ANC	absolute neutrophil count
AST	aspartate aminotransferase
AUC _{0-inf}	area under the concentration versus time curve from time 0 to infinite time
B2M	β2 microglobulin
BCL	B-cell lymphoma
BCL-X _L	B-cell lymphoma – extra large
BCRi	B-cell receptor inhibitor
BTK	Bruton's tyrosine kinase
CLL	chronic lymphocytic leukemia
C _{max}	observed maximum concentration
CoV	coronavirus
COVID-19	coronavirus disease – 2019
CR	complete remission
CrCL	creatinine clearance
CRi	complete remission with incomplete bone marrow recovery
CT	computed tomography
CTCAE	Common Terminology Criteria for Adverse Events
C _{trough}	trough concentrations
CYP	cytochrome P450
DNA	deoxyribonucleic acid
DTP	direct-to-patient
ECG	electrocardiogram
ECOG	Eastern Cooperative Oncology Group
eCRF	electronic case report form
FAS	Full Analysis Set
GCP	Good Clinical Practice

G-CSF	granulocyte-colony stimulating factor
GLP	Good Laboratory Practice
HIV	human immunodeficiency virus
ICH	International Council for Harmonisation
IEC	Independent Ethics Committee
IRB	Institutional Review Board
IRT	Interactive Response Technology
IV	intravenous
K _i	inhibition rate constant
MCL	myeloid cell leukemia
MRD	minimal residual disease
NCI	National Cancer Institute
NCI	National Cancer Institute
NHL	non-Hodgkin's lymphoma
OATP	organic anion-transporting polypeptide
ORR	overall response rate
PFS	progression-free survival
P-gp	P-glycoprotein
PO	oral
PR	partial response
QD	once daily
RNA	ribonucleic acid
R/R	relapsed or refractory
SAE	serious adverse event
SAP	Statistical Analysis Plan
SARS	severe acute respiratory syndrome
SLL	small lymphocytic lymphoma
SUSAR	Suspected Unexpected Serious Adverse Reaction
TA MD	Therapeutic Area Medical Director
TLS	tumor lysis syndrome
TP53	tumor protein p53
T-PLL	T-cell prolymphocytic leukemia
ULN	upper limit of normal
US	United States

APPENDIX D. DEFINITIONS OF LABORATORY AND CLINICAL TUMOR LYSIS SYNDROME

Metabolic Abnormality	Criteria for Classification of Laboratory Tumor Lysis Syndrome	Criteria for Classification of Clinical Tumor Lysis Syndrome
Hyperuricemia	Uric acid > 8.0 mg/dL (475.8 μmol/L) in adults or above the upper limit of the normal range for age in children	
Hyperphosphatemia	Phosphorus > 4.5 mg/dL (1.5 mmol/L) in adults or > 6.5 mg/dL (2.1 mmol/L) in children	
Hyperkalemia	Potassium > 6.0 mmol/liter	Cardiac dysrhythmia or sudden death probably or definitely caused by hyperkalemia
Hypocalcemia	Corrected calcium < 7.0 mg/dL (1.75 mmol/L) or ionized calcium < 1.12 mg/dL (0.3 mmol/L) ^a	Cardiac dysrhythmia, sudden death, seizure, neuromuscular irritability (tetany, paresthesias, muscle twitching, carpopedal spasm, Trousseau's sign, Chvostek's sign, laryngospasm, or bronchospasm), hypotension, or heart failure probably or definitely caused by hypocalcemia
Acute kidney injury ^b	Not applicable	Increase in the serum creatinine level of 0.3 mg/dL (26.5 μmol/L) (or a single value > 1.5 × the upper limit of the age-appropriate normal range if no baseline creatinine measurement is available) or the presence of oliguria, defined as an average urine output < 0.5 mL/kg/hr for 6 hrs

a. The corrected calcium level in mg/dL = measured calcium level in mg/dL + 0.8 × (4-albumin in g/dL).

b. Acute kidney injury is defined as an increase in the creatinine level of at least 0.3 mg/dL (26.5 μmol/L) or a period of oliguria lasting 6 hours or more. By definition, if acute kidney injury is present, the subject has clinical tumor lysis syndrome.

Note: In laboratory tumor lysis syndrome, 2 or more metabolic abnormalities must be present during the same 24-hour period within 3 days before the start of therapy or up to 7 afterward. Clinical tumor lysis syndrome requires the presence of laboratory tumor lysis syndrome plus an increased creatinine level, seizures, cardiac dysrhythmia, or death.

Source: Howard SC, Jones DP, Pui CH. The tumor lysis syndrome. *N Engl J Med.* 2011;364(19):1844-54.

APPENDIX E. RECOMMENDATIONS FOR INITIAL MANAGEMENT OF ELECTROLYTE ABNORMALITIES AND PREVENTION OF TUMOR LYSIS SYNDROME

Abnormality	Management Recommendations
Hyperkalemia (Including Rapidly Rising Potassium)	
Potassium \geq 0.5 mmol/L increase from prior value (even if potassium within normal limits [WNL])	
 • Recheck potassium, phosphorus, uric acid, calcium and creatinine in 1 hour STAT. If further \geq 0.2 mmol/L increase in potassium, but still < upper limit of normal (ULN), manage as per potassium \geq ULN. Otherwise recheck in 1 hour. • Resume per protocol testing if change in potassium is < 0.2 mmol/L, and potassium < ULN, and no other evidence of tumor lysis. • At the discretion of the investigator, may recheck prior to hospitalization. If stable or decreased, and still WNL, hospitalization is at the discretion of the investigator. Potassium, phosphorus, uric acid, calcium and creatinine must be rechecked within 24 hours.
Potassium > upper limit of normal	
 • Perform STAT ECG and commence telemetry. • Nephrology (or other acute dialysis service) notification with consideration of initiating dialysis. • Administer Kayexalate 60 g (or Resonium A 60 g). • Administer furosemide 20 mg IV \times 1. • Administer calcium gluconate 100 to 200 mg/kg IV slowly if there is ECG/telemetry evidence of life-threatening arrhythmias. • Recheck potassium, phosphorus, uric acid, calcium and creatinine in 1 hour STAT. • If potassium < ULN 1 hour later, repeat potassium, phosphorus, uric acid, calcium and creatinine 1, 2 and 4 hours, if no other evidence of tumor lysis.

Abnormality	Management Recommendations

Potassium ≥ 6.0 mmol/L (6.0 mEq/L) and/or symptomatic (e.g., muscle cramps, weakness, paresthesias, nausea, vomiting, diarrhea)
	
 • Perform STAT ECG and commence telemetry. • Nephrology (or other acute dialysis service) assessment with consideration of initiating dialysis. • Administer Kayexalate 60 g (or Resonium A 60 g). • Administer furosemide 20 mg IV \times 1. • Administer insulin 0.1 U/kg IV + D25 2 mL/kg IV. • Administer sodium bicarbonate 1 to 2 mEq IV push. • If sodium bicarbonate is used, rasburicase should not be used as this may exacerbate calcium phosphate precipitation. • Administer calcium gluconate 100 to 200 mg/kg IV slowly if there is ECG/telemetry evidence of life-threatening arrhythmias. Do not administer in same IV line as sodium bicarbonate. • Recheck potassium, phosphorus, uric acid, calcium and creatinine every hour STAT.
Hyperuricemia	

Uric acid ≥ 8.0 mg/dL (476 μmol/L)
	
 • Consider rasburicase (dose based on local guidelines and/or institutional standards). • If rasburicase is used, sodium bicarbonate should not be used as this may exacerbate calcium phosphate precipitation. • Recheck potassium, phosphorus, uric acid, calcium and creatinine in 1-hour STAT.

Uric acid ≥ 10 mg/dL (595 μmol/L) OR Uric acid ≥ 8.0 mg/dL (476 μmol/L) with 25% increase and creatinine increase ≥ 0.3 mg/dL (≥ 0.027 mmol/L) from predose level
	
 • Administer rasburicase (dose based on local guidelines and/or institutional standards). 
 • When rasburicase is used, sodium bicarbonate should not be used as this may exacerbate calcium phosphate precipitation. • Notify nephrology (or other acute dialysis service). • Recheck potassium, phosphorus, uric acid, calcium and creatinine in 1 hour STAT. • If uric acid < 8.0 mg/dL 1 hour later, repeat potassium, phosphorus, uric acid, calcium and creatinine 2 and 4 hours, later, if no other evidence of tumor lysis.

Abnormality	Management Recommendations

Calcium \leq 7.0 mg/dL (1.75 mmol/L) AND Subject symptomatic (e.g., muscle cramps, hypotension, tetany, cardiac arrhythmias)
	
 • Administer calcium gluconate 50 to 100 mg/kg IV slowly with ECG monitoring. • Telemetry. • Recheck potassium, phosphorus, uric acid, calcium and creatinine in 1-hour STAT. 
 • If calcium normalized 1 hour later, repeat potassium, phosphorus, uric acid, calcium and creatinine 2 and 4 hours, later, if no other evidence of tumor lysis. • Calculate corrected calcium and check ionized calcium if albumin low.
Hyperphosphatemia	

Phosphorus \geq 5.0 mg/dL (1.615 mmol/L) with \geq 0.5 mg/dL (0.16 mmol/L) increase
	
 • Administer a phosphate binder (e.g., aluminum hydroxide, calcium carbonate, sevelamer hydroxide, or lanthanum carbonate). • Nephrology (or other acute dialysis service) notification (dialysis required for phosphorus \geq 10 mg/dL). • Recheck potassium, phosphorus, uric acid, calcium and creatinine in 1-hour STAT. 
 • If phosphorus $<$ 5.0 mg/dL 1 hour later, repeat potassium, phosphorus, uric acid, calcium and creatinine 2 and 4 hours, later, if no other evidence of tumor lysis.
Creatinine	

Increase \geq 25% from baseline
	
 • Start or increase rate of IV fluids. • Recheck potassium, phosphorus, uric acid, calcium and creatinine in 1 to 2 hours STAT.

ECG = electrocardiogram; IV = intravenous

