Antihyperuricemic agents: Oral uric acid-reducing agent (allopurinol except if contraindicated) should be administered 72 hours before first venetoclax dose to all subjects; rasburicase should be considered prophylactically if the subject's baseline uric acid is elevated, unless contraindicated.

Blood chemistry monitoring: Chemistry and hematology laboratory tests are to be performed upon admission the night before the first dose of venetoclax. The investigator's decision to proceed with venetoclax treatment initiation will be based on these laboratory values. Laboratory monitoring for TLS is to occur at time 0 (predose, within 4 hours before venetoclax administration) and 4, 8, 12, and 24 hours after each dose escalation (including the optional increase to 600 mg at Week 8 or thereafter) on real time (turnaround < 2 hours). A dose increase must not be allowed until the subject's 24-hour laboratory test results have been reviewed by investigator. Results from time 0 (predose) laboratory values will be collected and used as baseline to assess potential electrolyte abnormalities occurring after venetoclax administration. Results from time 0 (predose) on Day 1 are not required to be available prior to initiating venetoclax treatment.

Nephrology consultation: Nephrology (or other acute dialysis service) consultation should be considered upon admission per institutional standards at the investigators' discretion to ensure emergency dialysis is available and the appropriate staff is aware and prepared to handle any necessary intervention for TLS. Telemetry should also be considered.

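### Appendix E gives two instructions that exclude each other, with no rule of precedence, to a subject who meets both the potassium ≥ 6.0 mmol/L row and the upper uric acid row

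*Protocol*

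**What the plan says.** Three rows of the Protocol Appendix E table and one paragraph of Section 6.2 bear on this.

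- **Potassium row.** The trigger is "Potassium ≥ 6.0 mmol/L (6.0 mEq/L) and/or symptomatic". Among the actions listed is "Administer sodium bicarbonate 1 to 2 mEq IV push", followed by "If sodium bicarbonate is used, rasburicase should not be used as this may exacerbate calcium phosphate precipitation".
- **Upper uric acid row.** The trigger is "Uric acid ≥ 10 mg/dL", or at least 8.0 mg/dL with a 25% increase and a creatinine increase of at least 0.3 mg/dL from the predose level. The action is "Administer rasburicase (dose based on local guidelines and/or institutional standards", followed by "When rasburicase is used, sodium bicarbonate should not be used as this may exacerbate calcium phosphate precipitation".
- **Lower uric acid row** (at least 8.0 mg/dL). The action is weaker: "Consider rasburicase (dose based on local guidelines and/or institutional standards". It carries the same warning against bicarbonate if rasburicase is used.
- **Section 6.2, antihyperuricemic agents.** Before venetoclax starts, "rasburicase should be considered prophylactically if" baseline uric acid is raised, unless contraindicated. The paragraph does not mention bicarbonate or refer to Appendix E.

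Neither the protocol nor the SAP says which row takes precedence when more than one applies.

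**The concern.** The two stronger rows each tell the site to give a drug, and each says the other row's drug should then not be given. Read one row at a time, the table is clear. Read for a subject who meets both rows, it is not: the site must either give a combination that the table itself warns may worsen calcium phosphate precipitation, or leave out a treatment that the table says to administer.

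The setting makes this worth correcting. Section 6.2 sends the reader to Appendix E for electrolyte changes that need prompt management, describes potassium increases as potentially life-threatening, and manages every subject as high risk because the ramp-up is short. TLS is also an adverse event of special interest (Section 6.1). A site using the table in that situation would have to supply the missing rule itself.

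**Working it through.** No sample size, power or error rate is involved, and the plan states no figure to reproduce. The check sets the rows side by side and asks, for each combination, whether any course of action satisfies everything that applies.

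**Inputs (Protocol Appendix E)**

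| Row | Bicarbonate | Rasburicase |
|---|---|---|
| Potassium ≥ 6.0 mmol/L and/or symptomatic | administer | not if bicarbonate is used |
| Uric acid, upper row | not when rasburicase is used | administer |
| Uric acid, lower row (≥ 8.0 mg/dL) | not if rasburicase is used | consider |

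**Step 1. Potassium row with the lower uric acid row only.** Bicarbonate is given; rasburicase is considered and not given. Both rows are satisfied, so there is no conflict.

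**Step 2. Potassium row with the upper uric acid row.** There are 2 × 2 = 4 possible courses:

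- both drugs: breaches the exclusion in each row;
- bicarbonate only: omits the upper uric acid row's drug;
- rasburicase only: omits the potassium row's drug;
- neither: omits both.

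None of the four satisfies both rows as written.

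**Step 3. Prior prophylactic rasburicase.** Suppose rasburicase was given under Section 6.2 and potassium later reaches 6.0 mmol/L. The potassium row says to administer bicarbonate. The uric acid rows say bicarbonate should not be used with rasburicase, but set no time limit and do not say whether an earlier prophylactic dose counts. The text leaves this open. It is less sharp than Step 2, because the prophylaxis is only to be considered.

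**Step 4. Can the two triggers coincide?** Appendix D defines laboratory TLS as two or more metabolic abnormalities in the same 24-hour period, and lists uric acid above 8.0 mg/dL and potassium above 6.0 mmol/L among them. High potassium with high uric acid is therefore one way to meet the protocol's own definition. The second limb of the upper uric acid trigger also requires a creatinine rise of at least 0.3 mg/dL, which Appendix D classes as acute kidney injury. Together with laboratory TLS, that is clinical TLS. The overlap belongs to the condition the table addresses.

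**Step 5. Frequency.** It cannot be estimated. The documents give no rates for either abnormality in T-PLL. The one TLS rate quoted (clinical TLS below 1%, Section 4.2) comes from acute myeloid leukemia studies with a different ramp-up. At most 37 subjects will be enrolled.

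**The case against.** The strongest reply is that Appendix E is headed as recommendations, that its exclusions say *should not*, and that the one in the potassium row is conditional on bicarbonate being used. The warning appears in three rows, so the authors saw the interaction and flagged it in both directions. On that reading the rows offer alternatives. Both rows also bring in nephrology or an acute dialysis service, and Section 6.2 raises consultation on admission.

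Much of this stands. Calling the text an order and a prohibition would overstate it, and expert help is at hand. But the table grades its own language: it separates *consider* from *administer*, and in the potassium row it makes calcium gluconate conditional on ECG or telemetry evidence while leaving bicarbonate unconditional. If the rows are alternatives, the rule for choosing is what is missing, and a nephrology contact does not put it in the protocol.

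A reader might go further in four ways that the documents do not support.

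- *That any high uric acid creates the conflict.* Step 1 shows that the lower row does not.
- *That the bicarbonate dose is misprinted because some neighbouring doses are per kilogram.* Kayexalate and furosemide are fixed doses in the same row, and no second bicarbonate value appears anywhere. The text shows no contradiction in the unit.
- *That the table as a whole fails.* Other combinations of abnormalities, and the other actions in these two rows, are unaffected.
- *That TLS results would vary by site.* The SAP counts TLS by adverse event search terms (Section 7.2) and laboratory thresholds (Section 7.3). A subject with post-baseline potassium above 6.0 mmol/L and uric acid of 10 mg/dL or more within 24 hours already meets laboratory TLS before this treatment choice arises.

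**Conclusion.** The point holds in a narrow form. When the potassium row and the upper uric acid row both apply, Appendix E makes two recommendations that exclude each other and gives no precedence; the status of earlier prophylactic rasburicase is also unstated. This is an internal inconsistency in safety guidance. It does not touch the sample size, the primary endpoint or the analysis.

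Its size is one pairing of rows plus one related gap, with a frequency the documents do not allow anyone to estimate. The conclusion rests on reading *administer* as stronger than *consider*, as the table's own usage suggests, and on the absence of a precedence rule in the protocol and SAP text available. It should be corrected because it bears on subject safety and is cheap to resolve; no redesign is needed.

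**What to change.** The sponsor's medical lead should reconcile the potassium row and the upper uric acid row of Appendix E, so that the text states which instruction applies when a subject meets both. The same wording, or a cross-reference from Section 6.2, should say how rasburicase already given prophylactically affects the potassium row. This review takes no position on what the rule should be.

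The cost is a wording change and a notification to approximately 20 sites in 9 countries. Under Section 8.1, a protocol amendment needs ethics committee approval before it is implemented, so the change is best carried with the next one unless the medical lead judges it more urgent. It needs no new procedure, data collection or SAP change.

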APPENDIX F. RECOMMENDED DOSE REDUCTIONS RELATED TO DRUG TOXICITIES

Recommended Venetoclax Dose Modifications for Toxicities

Event	Occurrence	Action
Tumor Lysis Syndrome		
Blood chemistry changes or symptoms suggestive of TLS	Any	Withhold the next day's dose. If resolved within 24 to 48 hours of last dose, resume at the same dose.
		For any blood chemistry changes requiring more than 48 hours to resolve, resume at a reduced dose (see Table 4).
		For any events of clinical TLS, resume at a reduced dose following resolution (see Table 4).
		Dose reduction or interruption of companion study drug may occur at the discretion of the investigator.
Non-Hematologic Toxicities		
Grade 3 or 4 non-hematologic toxicities	1 st occurrence	Interrupt venetoclax. Once the toxicity has resolved to Grade 1 or baseline level, venetoclax therapy may be resumed at the same dose. No dose modification is required.
	2 nd and subsequent occurrences	Interrupt venetoclax. Follow dose reduction guidelines in Table 4 when resuming treatment with venetoclax after resolution. A greater dose reduction may occur at the discretion of the investigator.
Hematologic Toxicities		
Grade 3 or 4 neutropenia with infection or fever; or Grade 4 hematologic toxicities (except lymphopenia)	1 st occurrence	Interrupt venetoclax. To reduce the infection risks associated with neutropenia, G-CSF may be administered with venetoclax if clinically indicated. Once the toxicity has resolved to Grade 1 or baseline level, venetoclax therapy may be resumed at the same dose.
	2 nd and subsequent occurrence	Interrupt venetoclax. Consider using G-CSF as clinically indicated. Follow dose reduction guidelines in Table 4 when resuming treatment with venetoclax after resolution. Additional dose reductions may occur at the discretion of the physician.
Consider discontinuing venetoclax for subjects who require dose reductions to less than 100 mg for more than 2 weeks.		

G-CSF = granulocyte-colony stimulating factor; TLS = tumor lysis syndrome

Recommended Ibrutinib Dose Modifications for Toxicities

Event	Occurrence	Action
Any of the following potentially drug-related toxicities (refer to Section 6.2): 
 • Grade 3 or higher neutropenia with infection or fever • ANC < 500/μL • platelets < 50,000/μL in the presence of clinically significant bleeding (Grade \geq 2) • platelets < 25,000/μL • Grade 3 nausea or Grade 3 or 4 vomiting or diarrhea if persistent despite optimal antiemetic or antidiarrheal therapy • any other Grade 4 or unmanageable Grade 3 toxicity 	1 st occurrence	Withhold ibrutinib until recovery to Grade \leq 1 or baseline; may restart at original dose level.
	2 nd occurrence	Withhold ibrutinib until recovery to Grade \leq 1 or baseline; may restart at 1 dose level lower (i.e., dose reduction Level 1). Follow dose reduction guidelines in Table 5 .
	3 rd occurrence	Withhold ibrutinib until recovery to Grade \leq 1 or baseline; may restart at 1 dose level lower (i.e., dose reduction Level 2). Follow dose reduction guidelines in Table 5 .
	4 th occurrence	Discontinue study drug (i.e., dose reduction Level 3). Follow dose reduction guidelines in Table 5 .
Note: For hematologic toxicities, restart of ibrutinib may be considered once the toxicity has resolved to study entry criteria level or better.		

ANC = absolute neutrophil count

APPENDIX G. ACTIVITY SCHEDULE

The following table shows the required activities. The individual activities are described in detail in the Operations Manual Section 3. Allowed modifications due to COVID-19 are detailed within the Operations Manual.

Study Activities Table

Activity	Screen	Week 1										Week 4	Week 8	Week 12	Week 16	Week 24	≥ Week 36	Final Visit	Follow-Up	PTFU	Survival
	Day -28 to Day -4	Day -3	Day -2	Day -1	Day 1	Day 2	Day 3	Day 4	Day 5	Day 6	Day 1	Day 1	Day 1 (± 3 days)	Day 1 (± 3 days)	Day 1 (± 3 days)	Every 12 weeks Day 1 (± 3 days)		30-Day	Same as visit schedule	Every 6 months	
INTERVIEWS & QUESTIONNAIRES																					
Informed consent	✓																				
Eligibility criteria	✓																				
Medical/oncology history	✓																				
Drug and alcohol screen	✓																				
Eastern Cooperative Oncology Group	✓														✓			✓			
Adverse event assessment	✓	✓	✓	✓	✓	✓	✓	✓	✓	✓	✓	✓	✓	✓	✓	✓	✓	✓	✓	✓	
Prior/concomitant therapy	✓			✓	✓	✓	✓	✓	✓	✓	✓	✓	✓	✓	✓	✓	✓	✓	✓	✓	
Dispense/collect subject calendars/diaries and dosing instructions										✓	✓	✓	✓	✓	✓	✓	✓				
Survival assessment																					✓
Any new anticancer therapy																					✓
LABORATORY ASSESSMENTS & EXAMINATIONS																					
Physical examination	✓	✓									✓	✓	✓	✓	✓	✓	✓	✓	✓	✓	
Height (screening only) and weight	✓	✓								✓	✓	✓	✓	✓	✓	✓	✓	✓	✓	✓	
Physical examination (or ultrasound) for the clinical response assessment of lymph nodes and spleen	✓										✓	✓	✓	✓	✓	✓				✓	

Activity	Screen	Week 1									Week 4	Week 8	Week 12	Week 16	Week 24	≥ Week 36	Final Visit	Follow-Up	PTFU	Survival
	Day -28 to Day -4	Day -3	Day -2	Day -1	Day 1	Day 2	Day 3	Day 4	Day 5	Day 6	Day 1	Day 1	Day 1 (± 3 days)	Day 1 (± 3 days)	Day 1 (± 3 days)	Every 12 weeks Day 1 (± 3 days)		30-Day	Same as visit schedule	Every 6 months
Electrocardiogram	✓																			
Serum pregnancy test	✓																			
Urine pregnancy test				✓							✓	✓	✓	✓ Every 4 weeks			✓	✓		
Vital signs	✓			✓	✓	✓	✓	✓	✓	✓	✓	✓	✓	✓	✓	✓	✓	✓	✓	✓
Hematology/chemistry samples	✓			✓	✓	✓	✓	✓	✓	✓	✓	✓	✓	✓	✓	✓	✓	✓	✓	
Coagulation panel	✓																			
Tumor lysis syndrome risk assessment	✓																			
Tumor lysis syndrome laboratory samples					✓	✓	✓	✓	✓	✓		TLS monitoring if escalation of venetoclax to 600 mg occurs								
Computed tomography (±7 days)	✓										Week 24 and any time during the study to confirm CR/CRi based on laboratory test results and physical examination.							✓		
Bone marrow sample (±7 days)	✓ (optional)										If a CT scan indicates a CR/CRi, then a bone marrow aspirate and biopsy will be required as soon as possible to confirm the clinical response.							✓		
Clinical response assessment											✓	✓	✓	✓	✓	✓	✓		✓	
Pharmacokinetic blood samples (predose)											✓	✓								
Cheek swab for biomarker assessment	✓																			
Blood sample for biomarker assessment	✓			✓	✓					✓	✓	✓	✓	✓	✓	✓	✓		✓	

Activity	Screen	Week 1						Week 4	Week 8	Week 12	Week 16	Week 24	≥ Week 36	Final Visit	Follow-Up	PTFU	Survival				
	Day -28 to Day -4	Day -3	Day -2	Day -1	Day 1	Day 2	Day 3	Day 4	Day 5	Day 6	Day 1	Day 1	Day 1 (± 3 days)	Day 1 (± 3 days)	Day 1 (± 3 days)	Every 12 weeks Day 1 (± 3 days)		30-Day	Same as visit schedule	Every 6 months	
Rx TREATMENT																					
Dispense venetoclax and ibrutinib		✓							✓	✓	✓	✓	✓	✓	✓						
Hospitalization			✓	✓	✓	✓	✓	✓	✓												
Oral hydration		✓	✓																		
Oral antihyperuricemic agent		✓	✓																		
Intravenous hydration			✓	✓	✓	✓	✓	✓	✓												
Venetoclax dosing				Once daily until end of treatment																	
Ibrutinib dosing				Once daily until end of treatment																	

CR = complete remission; CRI = complete remission with incomplete blood count recovery; CT = computed tomography; PTFU = post-treatment follow-up

